10.10 Age

The age at consent will be determined as follows:

- If age is recorded in the eCRF then this will be the one used for analysis
- If only year of birth is known, Date of Birth is imputed to the 15 June of the year of birth and age is derived as:

$$\text{Age at Informed Consent (years)} = (\text{Date of Informed Consent} - \text{Date of Birth} + 1) / 365.25$$

However, if derived age is resolved to 17-year-old and inclusion criteria 6.1.1 is met then age will be set to 18 years.

Based on the above age will also be categorized as ≤ 18 , > 18 to ≤ 45 , > 45 to ≤ 65 and > 65 years old and labelled ≤ 18 , > 18 to ≤ 45 , ≥ 46 to ≤ 65 and > 65 years, respectively.

10.11 Body Mass Index

At each weight measurement, the Body Mass Index (BMI) will be derived using height collected at screening.

It is calculated using the following formula:

$$\text{BMI (kg/m}^2\text{)} = \text{Weight (kg)} / [\text{Height (cm)}] \times 0.01]^2$$

Based on the above value BMI will also be categorized as follows:

- < 18.5 as underweight;
- ≥ 18.5 and < 25.0 as normal or healthy weight;
- ≥ 25.0 and < 30.0 as overweight;
- ≥ 30.0 as obese.

10.12 Disease History

As part of Disease history description, the following parameters will be derived:

Time since diagnosis of MS (years)

$$(\text{Date of Informed consent} - \text{Date of MS diagnosis} + 1) / 365.25;$$

Age at diagnosis of MS (years)

$$(\text{year of MS diagnosis} - \text{year of Birth} + 1)$$

Time since onset of spasticity due to MS (years)

$$(\text{Date of Informed consent} - \text{Date of onset of spasticity due to MS} + 1) / 365.25;$$

Age at onset of spasticity due to MS (years)

$$(\text{year of onset of spasticity due to MS} - \text{year of Birth} + 1);$$

Time between MS diagnosis and onset of spasticity due to MS (years)

$$(\text{Date of onset of spasticity due to MS} - \text{Date of MS diagnosis} + 1) / 365.25;$$

Time between MS diagnosis and onset of spasticity due to MS (months)

$$(\text{Date of onset of spasticity due to MS} - \text{Date of MS diagnosis} + 1) / 30.4375.$$

The following conversion will be applied as appropriate:

- Time since last relapse (months) = Time since last relapse (years) * 12,
- Time since last relapse (months) = Time since last relapse (days) / 30.4375.

Age at diagnosis of MS and age at onset of spasticity due to MS are only using year because only year of birth is planned to be collected.

If date of MS diagnosis and/or date of onset of spasticity due to MS are unknown or partial, they will be imputed as follow:

- if only day is missing, it will be imputed to the 15th of the month,
- If day and month are missing, they will be imputed to the 30 June of the year,
- However, if any of these dates fall after the informed consent date, they will be set to the informed consent date. If the date of onset of spasticity due to MS before the date of MS diagnosis due to imputation rule, it will be set to the date of MS diagnosis.

10.13 Renal Function Formula

Estimated Glomerular filtration rate (eGFR)

For the purpose of summary, the eGFR collected by central laboratory will be used

eGFR will also be categorized as follows:

- ≥ 90 as normal,
- ≥ 60 and < 90 as mild reduction,
- ≥ 30 and < 60 as moderate reduction,
- ≥ 15 and < 30 as severe reduction,
- < 15 as end stage kidney failure.

10.14 Prior and Concomitant Medication Start/Stop Date Imputation Rule

Table 10.14-1 Imputation Rules for Partial Medication Dates (D = day, M = month, Y = year)

Parameter	Missing	Additional Conditions	Imputation
Start date for concomitant meds	D only	M and Y same as M and Y of first dose of study drug	Date of first dose of study drug
		M and/or Y not same as date of first dose of study drug	First day of month but should fall on or after first study drug intake or if impossible after informed consent date
	M and D	Y same as Y of first dose of study drug intake during Period 1 and 2	Date of first dose of study drug
		Y after Y of first dose of study intake during period 1 but same Y as 1 st study drug intake during Period 2	Date of first drug intake during period 2
		Y after Y of last study drug intake	The earliest date between date of last study drug intake and end of study date
	M, D, and Y	Not allowed by the system	Not applicable
Stop date for concomitant meds	D only	M and Y same as M and Y of last dose of study drug	The earliest date between date of last dose of study drug and end of study date
		M and/or Y not same as date of last dose of study drug	The earliest date between last day of month and end of study date
	M and D	Not allowed by the system	Not applicable
	M, D, and Y	Not allowed by the system	Not applicable

Meds = Medications.

Note: In all cases, if an estimated start date is after a complete stop date, use the first day of the stop date month.

Similarly, if the estimated stop date is before a complete or imputed start date, use the last day of the start day month.

10.15 Mobile Health Data Handling

Data downloaded from the Mobile Health platform (MHP) such has number of morning and evening sprays administered, NRS scales, number of spasm counts, C-SSRS questionnaire, MSSS-88 questionnaire have specific information to link the date MHP data were submitted to the date the data are referring to which have to be reported in SDTM and ADAM as detailed in **Error! Reference source not found..** In practice, any time the variable XGRID contains the term “Late” the date to be used refers to the day before the one coming from MHP.

Table 10.15-1 MHP data - Date Handling

XPGRID	Explanation
Initial on time Diary	Served from 6:00pm to 11:59 pm to the day a participant is moved to screening
Initial late Diary	Served from 12:00 am to 03:05 pm the next morning when the initial On Time Diary was NOT completed the previous day
On time diary	Served from 6:00pm to 11:59 pm when the Initial On Time, On time, or Missed On Time Diary was completed the previous day
Late diary	Served from 12:00 am to 03:05 pm when On Time Diary was NOT completed the previous day
Missed on time	Served from 6:00pm to 11:59 pm when an Initial Late, or Missed Late Diary was served on the same day
Missed late	Served from 12:00 am to 03:05 pm when the Missed On Time Diary was Not completed the previous day

10.16 Modified Ashworth Scale (MAS) Transformed Score

The MAS will be conducted and scored on 10 lower limb muscle groups (hip flexors and adductors, knee flexors and extensors, and plantar flexors) on the left and the right side of the body at Screening, Day 1 H0, Day 1 H3 and Day 21 each treatment period.

For the purpose of the analysis, the result of each of the 10 MAS scores will be transformed using the following algorithm: MAS untransformed [to MAS transformed] scores; 0[0], 1[1], 1+[2], 2[3], 3[4] and 4[5].

Each MAS transformed score is ranging from ‘0’ (No increase in muscle tone) to ‘5’ (Affected part rigid in flexion or extension).

These scores will then be used to derive 3 mean Lower Limb Muscle Tone (LLMT) measures at D1H0, Day 1 H3 and Day 21 of each treatment period.

- The LLMT-6: defined as the average of the 6 individual MAS transformed scores of knee flexors, knee extensors, and plantar flexors on both sides of the body. For any given patient, at a given visit, the LLMT-6 will be set to missing if individual MAS transformed scores are missing for 3 or more of the 6 specified muscle groups (as described in [Table 10.16-1](#)),
- The LLMT-10: defined as the average of the 10 individual MAS transformed scores of knee flexors, knee extensors, plantar flexors, hip flexors and hip adductors on both sides of the body. For any given

patient, at a given visit, the LLMT-10 will be set to missing if individual MAS transformed scores are missing for 5 or more of the 10 specified muscle groups (as described in [Table 10.16-1](#)),

- The LLMT-4 defined as the average of the 4 individual MAS transformed scores of knee flexors, knee extensors on both sides of the body. For any given patient, at a given visit, the LLMT-4 will be set to missing if individual MAS transformed scores are missing for 2 or more of the 4 specified muscle groups (as described in [Table 10.16-1](#)**Error! Reference source not found.**).

In addition, LLMT-6/LLMT-4/LLMT-10 scores derived with individual MAS transformed score missing in at least one muscle group will be identified.

Table 10.16-1 Lower Limb Muscle Tone - Missing Data Handling

Parameter	Number of items (muscle groups) included in score derivation	Minimum number of muscle group scores required for score derivation (at least 50%)
LLMT-4	4	3
LLMT-6	6	4
LLMT-10	10	6

LLMT-4 = Lower Limb Muscle Tone-4; LLMT-6 = Lower Limb Muscle Tone-6; LLMT-10 = Lower Limb Muscle Tone-10.

The change and percentage change from baseline will then be calculated (as respectively described in [Section 10.3](#) and in [Section 10.4](#)) for each LLMT score.

The percentage change from baseline values will also be categorized as $\leq -20\%$, $\leq -30\%$, $\leq -40\%$ and $\leq -50\%$ to assess an improvement of respectively $\geq 20\%$, $\geq 30\%$, $\geq 40\%$ and $\geq 50\%$

Although unlikely to occur as per inclusion criteria 6.1.5, if a baseline LLMT score is equal to 0, the percentage change from baseline will be imputed using the following formula:

- Percentage change from baseline $= (x+1)*100$, where x is the post baseline value .

Missing LLMT scores will be considered as not having met any of the improvement criteria (imputed as failure).

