### **6.1 Inclusion Criteria**

#### *Screening (Visit 1)*

For inclusion in the trial, patients must fulfill ALL of the following criteria:

- 6.1.1 Male or female, aged 18 years or above.
- 6.1.2 Willing and able to give informed consent for participation in the trial (see [Section 15.2](#)).
- 6.1.3 Willing and able (in the investigator's opinion) to comply with all trial requirements.
- 6.1.4 Has had a diagnosis with any disease subtype of MS, by revised 2017 McDonald criteria, for at least 12 months prior to Visit 1 and is expected to remain stable for the duration of the trial.
- 6.1.5 Has an MAS untransformed score of at least 2 in 2 or more of 6 muscle groups (right knee flexors, left knee flexors, right knee extensors, left knee extensors, right plantar flexors, or left plantar flexors) at Visit 1.
- 6.1.6 If currently receiving approved anti-spasticity therapy, it must be with a stable dosing regimen for at least 30 days prior to Visit 1. The patient must be willing to maintain the same antispasticity medication and not plan to initiate a new course of physiotherapy for the duration of the trial.
- 6.1.7 If currently receiving an approved MS disease-modifying therapy, it must be at a stable dose for at least 3 months prior to Visit 1 and is expected to remain stable for the duration of the trial.
- 6.1.8 If currently receiving dalfampridine or fampridine, it must be at a stable dose for at least 3 months prior to Visit 1 and is expected to remain stable for the duration of the trial.
- 6.1.9 Willing to allow the responsible authorities to be notified of participation in the trial, if mandated by local law.
- 6.1.10 Willing to allow his or her primary care practitioner (if he or she has one) and/or treating neurologist (if he or she has one) to be notified of participation in the trial, if the primary care practitioner/treating neurologist is different from the investigator.

*Additional Inclusion Criteria at Randomization (Visit 2)*

Patients are eligible for randomization in the trial if, in addition to continuing to meet the Screening (Visit 1) inclusion criteria, they also meet the following criterion prior to Visit 2 (Day 1):

6.1.11 Completed at least 5 of 7 days of their electronic diary reporting during the 7 days immediately preceding Visit 2 (Day 1).

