12.5.2.3.3 Summary Descriptions and Listings

LLMT-6 values, change from baseline and percentage change from baseline in LLMT-6 will be summarized by treatment arm, per treatment period and overall, over time.

Mean \pm SD LLMT-6 values and change from baseline by visit and treatment arm will be plotted.

Scatterplots of the change from baseline to Day 21 and percentage change from baseline to Day 21 in LLMT-6 against the baseline LLMT-6 will also be produced.

Spaghetti plots presenting baseline, Day 1 H3 and Day 21 LLMT-6 scores from both treatment periods will be plotted for each patient by treatment arm. Paneled by treatment period and the treatment received in that period differentiated by line pattern.

Cumulative distribution functions on change from baseline and relative change from baseline to Day 21 in LLMT-6 will be plotted by treatment arm.

A by-patient listing will be provided for LLMT-6 observed, change and relative change from baseline along with responder status (as defined in [Section 12.5.2.3.2](#)).

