12.5.3.2 Sensitivity Analysis: Tipping Point Analysis

The primary efficacy analysis on secondary endpoint assumes data are either missing at random or missing not at random as per missing data handling strategy described in [Section 12.5.2.1.3](#).

To assess the robustness of the treatment effect with regard to missing data, sensitivity analyses based on a tipping point analysis will be performed for the secondary efficacy endpoint to assess the impact of the missing data assumed MNAR on the secondary estimand.

This analysis will impute missing nabiximols Day 21 data under a Missing Not at Random approach, using the FAS during the 51-day randomized efficacy period (see [Section 10.1](#)).

Thus, when no penalty is added the tipping point analysis is equivalent to the primary analysis of the secondary endpoint.

This analysis will be conducted using the same approach as the one described for primary efficacy endpoint (see [Section 12.5.2.2](#)). However, as LLMT-4 score is based on 4 muscle groups (and not 6 muscle groups as LLMT-6) as described in [Section 12.5.2.2](#), the Step 5 (Step 2 to Step 4 will be repeated for a plausible $\delta_{\text{nabiximols}}$ value using a grid search method. Firstly larger changes in delta values (delta will range from 0 to 5 by increments of 5/4 where 5/4 represents the maximum effect of an individual MAS transformed score on LLMT-4) will be used. If the inference changes, then smaller changes in delta values (1/4 representing the change of 1 of LLMT-4 score) will be used to identify a more accurate tipping point between the last two delta values which were using larger changes (ie. last delta value with $p < 0.05$ and first delta value with $p \geq 0.05$).

The same tables, figures and listing as those performed for LLMT-6 (as described in [Section 12.5.2.3.3](#)) will be provided for LLMT-4.

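### The SAP's rule for a zero baseline scores an unchanged patient as +100%, and inclusion criterion 6.1.5 does not rule out a zero baseline for LLMT-4

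*SAP*

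**What the plan says.** SAP section 10.16 defines three averages of transformed MAS scores. LLMT-6 covers knee flexors, knee extensors and plantar flexors on both sides. LLMT-10 adds the hip flexors and adductors. LLMT-4 covers the four knee groups only. For each score, "The change and percentage change from baseline will then be calculated". The ordinary formula, in SAP section 10.4, divides change by baseline and so is undefined at a baseline of 0.

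For that case section 10.16 adds: "Although unlikely to occur as per inclusion criteria 6.1.5, if a baseline LLMT score is equal to 0, the percentage change from baseline" is imputed as (x+1)×100, "where x is the post baseline value".

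The criterion it relies on is Protocol 6.1.5: "Has an MAS untransformed score of at least 2 in 2 or more of 6 muscle groups". The list of six ends with "right plantar flexors, or left plantar flexors) at Visit 1", so both plantar flexors count.

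Percent change feeds planned outputs. SAP section 12.5.2.3.3 states that "LLMT-6 values, change from baseline and percentage change from baseline in LLMT-6 will be summarized by treatment arm", and it also plans scatterplots, cumulative distribution plots and a by-patient listing. SAP section 12.5.3.2 carries these over to the secondary endpoint: "The same tables, figures and listing as those performed for LLMT-6" are to be produced for LLMT-4.

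**The concern.** There are two separate problems. First, the rule gives a wrong value in the simplest case: no change is reported as +100%, the figure that the ordinary formula gives to a patient whose score doubles. Second, the reason given for expecting few such cases does not apply to LLMT-4. Criterion 6.1.5 draws on six muscle groups, and LLMT-4 leaves out two of them.

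At stake are the descriptive percent-change results for the secondary efficacy endpoint. They could show worsening that did not happen.

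**Working it through.** **Inputs.** The zero-baseline rule, the MAS transformation (untransformed 2 becomes 3, and 0 stays 0) and the score definitions come from SAP section 10.16. The ordinary percent-change formula is in SAP 10.4 and the definition of baseline in SAP 10.2. Eligibility is Protocol 6.1.5. The 170 completers and roughly 190 randomized patients are in SAP 8.2.

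**1. The rule as written, against a consistent offset.** If +1 is added to avoid dividing by zero, it belongs on both sides: ((x+1)/(0+1) − 1)×100 = x×100.

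| Later score x | SAP rule (x+1)×100 | Offset on both sides, x×100 | Difference |
|---|---|---|---|
| 0 | +100% | 0% | 100 |
| 0.25 | +125% | +25% | 100 |
| 1 | +200% | +100% | 100 |
| 5 | +600% | +500% | 100 |

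The SAP rule is 100 points higher at every x. For comparison, the ordinary formula gives a patient who stays at 0.25 a change of 0%, and a patient who goes from 0.25 to 0.50 a change of (0.50 − 0.25)/0.25×100 = +100%.

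**2. What 6.1.5 guarantees.** Take complete scores that just meet the criterion: two groups at transformed score 3 and all others at 0.

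- LLMT-6: (3+3)/6 = 1.00
- LLMT-10: (3+3)/10 = 0.60
- LLMT-4, when the two qualifying groups are the plantar flexors: 0/4 = 0.00

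Enumerating all 6^6 = 46,656 patterns of the six groups, 41,553 meet 6.1.5 and 9 of those have LLMT-4 = 0 (each plantar flexor at 3, 4 or 5, so 3×3). This shows only that the case is possible. Patterns are not equally common in patients, so 9 in 41,553 is not a prevalence.

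**3. Timing.** Criterion 6.1.5 is tied to Visit 1, while the baseline in SAP 10.2 is the last pre-dose value of each period. For LLMT-6 or LLMT-10 to be 0, scores would have to fall after Visit 1 or the qualifying groups would have to be missing at baseline. LLMT-4 needs neither.

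**4. Size.** Compared with coding no change as 0%, one unchanged zero-baseline patient-period moves an arm's mean percent change by 100/N: 100/170 = 0.59 points, or 100/190 = 0.53. The documents give no frequency, so the counts below are assumptions, at N = 190:

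| Unchanged zero-baseline patients | Shift in arm mean (points) |
|---|---|
| 1 | +0.5 |
| 5 | +2.6 |
| 10 | +5.3 |
| 19 | +10.0 |

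As an illustration, suppose that 180 patients are at −10% and 10 are unchanged at 0. The SAP rule gives (10×100 − 180×10)/190 = −4.2%. Coding the ten as 0% gives −1,800/190 = −9.5%. Leaving them out gives −10.0%. The SD also rises, because the ten lie 110 points from the rest.

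The SAP addendum records that the study stopped short of planned recruitment, so each patient weighs more: 1.0, 2.0 or 3.3 points at an assumed N of 100, 50 or 30.

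**The case against.** The strongest reply is that very little depends on this rule, and most of that reply stands.

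- The SAP calls a zero baseline unlikely, not impossible, and provides a rule for it. Showing that LLMT-4 can be 0 does not contradict that. What fails is the reason given, as far as it concerns LLMT-4.
- The tests of LLMT-6 and LLMT-4 use absolute change (SAP 12.5.2.1.8 and 12.5.3.1), so they do not use the rule.
- Responder status is unaffected. A patient at 0 cannot show a reduction of 20% or more under any rule, and the responder models in SAP 12.5.2.3.2 are for LLMT-6 only.
- In a crossover, a patient unchanged at 0 in both periods adds the same +100 points to each arm, so the shift cancels in the comparison. It does not cancel for a patient at 0 in one period only, and the arm-level means stay too high either way.
- Medians and quartiles are also planned (SAP 12.0), and a few values at +100% barely move them. The scatterplots against baseline and the listings would show these patients individually.
- The addendum may have removed the issue. It keeps descriptive statistics but drops supplementary analyses and imputation for missing data, and SAP 12.5.2.3.3 sits under a supplementary heading. Against that, an observed baseline of 0 is not missing data, and the addendum does not mention percent change. Whether these summaries survive is unclear.

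**Conclusion.** The rule is wrong as written, and criterion 6.1.5 does not protect LLMT-4 from it. The consequence is conditional and minor. If zero LLMT-4 baselines occur, the arm-level mean and SD of LLMT-4 percent change, and the related plots and listings, would be distorted, by 100/N points in the mean per unchanged patient-period (about 0.6 at N = 170). This rests on complete scores at baseline, on an unknown number of such patients, and on the percent-change outputs still being produced under the addendum.

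A reader might infer that the LLMT-4 summaries are distorted in fact, or that the secondary endpoint result is biased. The documents support neither: they give no count of zero baselines, and the test uses absolute change. Nor is the weakness common to all scores other than LLMT-6, since LLMT-10 contains the plantar flexors and has a minimum of 0.60 under the same conditions.

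**What to change.** Replace the rule in SAP section 10.16 with one that treats all zero-baseline patients alike: percent change is not calculable whenever the baseline LLMT score is 0, whatever the later value. Report by arm the number of such patients and their absolute change.

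A tempting alternative is to code 0% when both values are 0 and leave percent change not calculable only when the later value is above 0. That should be avoided. From a baseline of 0 a score can only stay or rise, so this would keep the unchanged patients and drop exactly those who worsened, which selects on outcome.

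The cost is one line in the SAP and no new data. A few patients leave the percent-change summary but stay in the absolute-change summaries and tests.

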10.17 Timed 25-Foot Walk

The T25FW is the time needed for a patient to walk 25-feet and will be performed at Day 1 H0 and Day 21 of each treatment period. The test consists of two trials separated by a 5-minute rest period. The maximum duration of each trial is set to 3 minutes (180 seconds).

The average T25FW (expressed in seconds) will be derived for each patient as the average of the two trials..

If a patient only performs 1 of the 2 trials at a given analysis day, the unperformed trial will be imputed using the highest T25FW (180 seconds) to perform the main analysis. An exploratory analysis will also be conducted without imputing unperformed trial as missing thus, leading to a missing average T25FW.

If a patient is not using the same device or is introducing a device within a given treatment period, the average T25FW will be set to missing.

The change and percentage change from baseline will then be calculated (as respectively described in [Section 10.3](#) and in [Section 10.4](#)).

The percentage change from baseline will be categorized as $\leq -20\%$ and $> 20\%$ to assess respectively $\geq 20\%$ improvement (as response) and $< 20\%$ improvement (as non-response) using imputed T25FW (as described above).

Missing average T25FW will be considered as not having met the improvement criteria (imputed as failure).

10.18 11-point Numerical Rating Scale Score (NRS-Spasticity Score)

The 7-day average 11-point NRS spasticity score will be derived for each patient as the mean NRS-spasticity score recorded in the eDiary during the last 7 days preceding Period 1 Day 1 H0 (Baseline), and Day 15 and Day 21 of each treatment period as follows:

$$\frac{\text{Sum of the NRS spasticity scores during the 7 - day period}}{\text{Number of days in which the daily diary was completed during the 7 - day period}}$$

For each assessment timepoint, the 7-day average 11-point NRS-spasticity score will be set to missing if scores are missing for 4 days or more in total or for 3 consecutive days within each 7-day period.

In case of the diary data are available but the visit does not take place the target visit date will be used.

On-treatment / off-treatment assessment

A 7-day average 11-point NRS spasticity score will be considered on-treatment if derived using only post baseline daily scores collected on or before the date of IMP discontinuation and will be considered off-treatment otherwise.

In case of IMP discontinuation, if possible with regards to missing data rule specified just above, the 7-day average 11-point NRS spasticity score considered on-treatment will also be derived using only post-baseline scores collected on or before the date of IMP discontinuation.

The change from baseline will then be calculated (as respectively described in [Section 10.3](#)).

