#### **9.2.15.4 Timed 25-Foot Walk**

The T25FW is a quantitative measure of lower extremity function. A blinded, independent, trained, and certified healthcare professional will perform the T25FW. The same assessor should administer the T25FW test throughout the trial where possible. If ambulatory, the patient will be instructed to begin at one end of a clearly marked 25-foot course. They will be instructed to walk the 25 feet as quickly as possible, but safely, and to not slow down until after they have passed the finish line. The task will be immediately administered a second time following the first trial by having the patient walk back the same distance.

Patients will be permitted to use their customary, nonmotorized assistive device (AD) (cane, walking sticks, walker, and rollator) during the T25FW test. The same AD must be used at each assessment and its use documented in the patient record.

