	without major IPD impact)	
IES:
 
Regardless permanent treatment discontinuation
 
Regardless premature study discontinuation
 
Without major IPD
 
Accounting for COVID-19 impact
 
PLS: Mean difference between nabiximols and placebo
 
Analysis: LSMD from CFB linear mixed-effect model for crossover data adjusted on period baseline LLMT-10 with placebo-based MI under MNAR assumption.

	E1, SUP6 (Supplementary without COVID-19 impact)	
Variable: Change from period baseline in LLMT-10 at Day 21
 
Population: FAS
 
IES:
 
Regardless permanent treatment discontinuation
 
Regardless premature study discontinuation
 
Regardless major IPD
 
Without COVID-19 impact
 
PLS: Mean difference between nabiximols and placebo
 
Analysis: LSMD from CFB linear mixed-effect model for crossover data adjusted on period baseline LLMT-10 with placebo-based MI under MNAR assumption.

Exploratory Objective: To evaluate the effect of nabiximols after administration of multiple doses on walking using the Timed 25-Foot Walk (T25FW) test.
		
T25FW	E2, Primary	
Variable: Change from period baseline in average 25-foot walk time at Day 21
 
Population: FAS
 
IES:
 
Regardless permanent treatment discontinuation
 
Regardless premature study discontinuation
 
Regardless major IPD
 
Regardless COVID-19 impact
 
PLS: Mean difference between nabiximols and placebo
 
Analysis: LSMD from CFB linear mixed-effect model for crossover data adjusted on period baseline average T25FW. Single imputation at trial level: missing trial time are imputed to 180 seconds under MAR assumption

	E2, S1 (without missing trial time imputation)	Variable: Change from period baseline in average 25-foot walk time at Day 21 Population: FAS IES: Regardless permanent treatment discontinuation Regardless premature study discontinuation Regardless major IPD Regardless COVID-19 impact PLS: Mean difference between nabiximols and placebo Analysis: LSMD from CFB linear mixed-effect model for crossover data adjusted on period baseline average T25FW. No imputation under MAR assumption

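### The 180-second value for an unperformed T25FW trial also applies at baseline, where it creates false improvement, and the responder analysis has no version without it

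*SAP*

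**What the plan says.** SAP 10.17 states that the T25FW "will be performed at Day 1 H0 and Day 21 of each treatment period", so each period has a baseline and an end-of-period measurement. The visit score "will be derived for each patient as the average of the two trials". Each trial has a cap: "The maximum duration of each trial is set to 3 minutes (180 seconds".

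The missing-trial rule opens with "If a patient only performs 1 of the 2 trials at a given analysis day" and continues that "the unperformed trial will be imputed using the highest T25FW (180 seconds) to perform the main analysis". It does not separate baseline from Day 21, does not ask why the trial was not done, and ignores the time of the completed trial. Section 10.17 then derives change and percentage change, and specifies that the 20% responder classification uses the imputed times.

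Appendix 14 repeats the rule for the main T25FW analysis (E2 Primary): "Single imputation at trial level: missing trial time are imputed to 180 seconds under MAR assumption". Section 12.5.5.1 and Appendix 14 E2 S1 plan a repeat of the mean-change model without imputation, in which the visit average is missing if one trial was not done. No such repeat is planned for the responder analysis (E2 SUP1).

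The documents also describe the test differently. In the SAP, "The test consists of two trials separated by a 5-minute rest period". In protocol 9.2.15.4, "The task will be immediately administered a second time following the first trial".

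The SAP addendum (section 7.0), written after the decision to stop the study early, keeps T25FW for listings only, with no summary or inferential statistics.

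**The concern.** A fixed worst value is usually defended as conservative: a patient who cannot finish the test is scored as badly as possible. That holds only after baseline. SAP 12.5.5.1 treats a shorter time as improvement, so an inflated baseline followed by an ordinary Day 21 time reads as a large benefit. The same gap in the data therefore penalises a patient at one visit and rewards the same patient at the other.

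The rule also orders patients oddly. Someone with neither baseline trial has a missing average and counts as a non-responder. Someone with one baseline trial and no real change will usually count as a responder.

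At stake is the responder count for the trial's only performance-based walking measure and, to a lesser extent, its mean change. The error favours whichever treatment was given in the period with the incomplete baseline.

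**Working it through.** The plan gives no T25FW result, power or expected walk time, so there is no figure to reproduce. The check is direct arithmetic on the stated rule.

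**Inputs**
- Imputed value: 180 s (SAP 10.17).
- Visit score: (trial 1 + trial 2)/2 (SAP 10.17).
- Percentage change: 100 × (Day 21 - baseline)/baseline (SAP 10.4).
- Response: a reduction of at least 20% (SAP 10.17, 12.5.5.1).
- True time T, the same at every performed trial: an assumption, varied from 5 to 120 s.

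**Formulas for an unchanged walker**
- Score with one trial unperformed: A = (T + 180)/2.
- Gap at baseline only: 100 × (T - A)/A.
- Gap at Day 21 only: 100 × (A - T)/T.

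Worked case, T = 10 s: A = (10 + 180)/2 = 95 s. Gap at baseline: (10 - 95)/95 = -89.5%. Gap at Day 21: (95 - 10)/10 = +850%.

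| True time T (s) | Score A (s) | Gap at baseline | Gap at Day 21 |
|---|---|---|---|
| 5 | 92.5 | -94.6% | +1750% |
| 10 | 95 | -89.5% | +850% |
| 20 | 100 | -80.0% | +400% |
| 30 | 105 | -71.4% | +250% |
| 60 | 120 | -50.0% | +100% |
| 120 | 150 | -20.0% | +25% |

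**Where the false response ends.** Response needs T ≤ 0.8 × (T + 180)/2, that is 0.6T ≤ 72, so T ≤ 120 s. Every unchanged walker at 120 s or faster with one missing baseline trial is a responder. Above 120 s the sign is the same but the criterion is not met: at 150 s the false change is -9.1%.

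**Real change is overridden too.** A 10-s walker with one missing baseline trial stays a responder up to a Day 21 time of 0.8 × 95 = 76 s. A patient who truly improves from 10 s to 7 s but misses one Day 21 trial scores (7 + 180)/2 = 93.5 s, or +835%.

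**Cancellation.** If one trial is missing at both visits, an unchanged walker scores A twice and the change is 0%.

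**Comparison within the SAP.** Other scores use what was observed. The NRS average divides by the days completed (10.18), MSSS-88 fills gaps with the mean of the answered items (10.20), and LLMT-6 can be formed from 4 of 6 muscle groups (10.16). For T25FW, the main analysis overrides the completed trial with a 180-s partner and the sensitivity analysis discards it.

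**The case against.** The strongest objection is that the consequence has largely gone. The addendum removes every T25FW summary and test, and the endpoint was exploratory and outside the testing hierarchy. A reader might infer that reported T25FW results will be distorted; the documents do not support that. What survives is narrower. The addendum keeps listings, and 12.5.5.1 describes the T25FW listing as holding both observed and derived variables. It does not say whether derived averages are kept or dropped.

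Second, a safeguard exists. The mean-change model is repeated without imputation on the Full Analysis Set, and a non-parametric analysis follows if residuals look non-normal. This answers much of the worry about mean change, and it would be wrong to say that result rests on imputed values alone. Neither provision reaches the responder analysis.

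Third, the percentages are illustrations. Nothing in the documents shows how fast these patients walk or how often only one trial is done. One 10-s walker would shift a raw mean over 170 completers by 85/170 = 0.5 s, but that is not the effect on the estimated treatment difference. The model adjusts for the period baseline, which is itself inflated, and patients who cannot walk are exempt from the test, so 170 is not the denominator.

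Fourth, two wording points are easily overstated. The response classes are printed as ≤ -20% and > 20%, from which a reader might infer that anyone between is unclassified. The same sentence defines non-response in words as under 20% improvement, so this is a dropped minus sign. The missing-at-random label in Appendix 14 does not describe a fixed 180-s value, but most of the other exploratory entries use the phrase for the model's treatment of missing visits; it is loose wording.

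Finally, using the completed trial gives a patient too tired to repeat the walk credit for the first one. That is a fair cost, though small beside a false improvement of 20% or more.

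**Conclusion.** The point holds, at low severity. The 180-s rule applies at baseline by its own wording and acts in the patient's favour there, so it cannot be defended as conservative. For unchanged walkers with assumed true times of 5 to 120 s, one missing baseline trial gives -94.6% to -20%, always a response; one missing Day 21 trial gives +1750% to +25%. The direction does not depend on the assumed time for anyone faster than 180 s; the size does. How often this would occur is unknown.

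The planned repeat without imputation limits the harm to mean change but leaves the responder analysis exposed. Under the addendum, the practical effect is confined to derived averages and changes in listings and to any later use of this derivation. The difference between the two test descriptions is a real but minor mismatch; it does not show that a skipped trial has no consistent meaning.

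**What to change.** - In SAP 10.17 and Appendix 14 E2, do not assign 180 s at baseline. When only one trial was performed at a visit, use its time as the visit value. The unchanged walker in the table then has a change of 0% in both scenarios.
- Keep the 180-s version, at Day 21 only, as a sensitivity analysis, and run it for the responder analysis as well as mean change. This shows how much depends on crediting a tired patient with the first walk.
- Correct the non-response cut-off in 10.17 from > 20% to > -20%.
- Align the SAP's account of the two trials with protocol 9.2.15.4, and drop the missing-at-random label from the 180-s entry in Appendix 14.
- For the listings that remain under the addendum, print the observed time of each trial and flag or omit any average containing an imputed 180 s.

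The cost is a short derivation change and some SAP wording. No new data are needed, because the rule turns only on whether each trial was performed.
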